14 NOTIFICATION OF SERIOUS BREACHES

In accordance with the Medicines for Human Use (Clinical Trials) Regulations 2004 and its amendments, the Sponsor of the trial is responsible for notifying the licensing authority in writing of any serious breach of the conditions and principles of GCP in connection with that trial or of the protocol relating to that trial, within 7 days of becoming aware of that breach. For the purposes of this regulation, a "serious breach" is defined a breach which is likely to affect the:

Safety or physical or mental integrity of the patients of the trial;

Scientific value of the trial

Sites are therefore requested to notify the ABBRUPT Trial Office of any suspected trial-related serious breach of GCP and/or the trial protocol as soon as they become aware of them. Where the ABBRUPT Trial Office is investigating whether or not a serious breach has occurred, sites are also requested to co-operate with the ABBRUPT Trial Office in providing sufficient information to report the breach to the MHRA where required and in undertaking any corrective and/or preventive action.

Sites may be suspended from further recruitment in the event of serious and persistent non-compliance with the protocol and/or GCP, and/or poor recruitment.

15 END OF TRIAL DEFINITION

The end of trial will be 6 months after the date of the last data capture including resolution of DCFs. This will allow sufficient time for the completion of protocol procedures, data collection and input and data cleaning. The Trial Office will notify the REC, MHRA and the Sponsor within 90-days of the end of trial. Where the trial has terminated early, the Trial Office will notify the MHRA REC within 15 days of the end of trial. The Trial Office will provide the REC, MHRA and the Sponsor with a summary of the clinical trial report within 12 months of the end of trial.

16 STATISTICAL CONSIDERATIONS

16.1 Sample size

Sample size calculation is based on a time-to-event superiority analysis. Literature (8) suggests that 90-day mortality in patients with NOAF was approximately 20%. A 5% absolute difference in mortality is considered a 'meaningful clinically important difference [MCID]' which equates to a hazard ratio of approximately 0.73. Using 90% power and a 2-sided alpha of 0.05 to detect a hazard ratio of 0.73 with event rate of 20% (or survival rate of 80%), a total of 426 events will be required. The enrolment of approximately 2430 patients would provide the required number of primary outcome events. Allowing for a 5% non-evaluable rate, a total of 2560 patients (1280 per group) will need to be recruited (rounded to nearest 10). We have allowed for a slightly higher non-evaluable rate as this study is recruiting critically ill patients undergoing an acute deterioration during their care.

16.2 Analysis of outcomes

A separate Statistical Analysis Plan will be produced and will provide a more comprehensive description of the planned statistical analyses. A brief outline of the planned analyses is given below.

The primary comparison groups will be composed of those randomised to Amiodarone versus those randomised to Beta blockade. All analyses will be based on the intention to treat principle, i.e., all patients will be analysed in the intervention group to which they were randomised irrespective of adherence to randomised intervention or protocol deviations. For all outcomes, appropriate summary statistics will be presented by group, (e.g. proportions/percentages, mean/standard deviation or median/interquartile range). Intervention effects will be adjusted for the minimisation variables listed in Section 6.5 **ENROLMENT, RANDOMISATION and BLINDING** as fixed effects in the model (except site/hospital which will be included as a random effect). 95% confidence intervals and p-values will be presented for all outcomes. No adjustment for multiple comparisons will be made.

16.3 Primary outcome(s)

Differences in the primary outcome (90-day mortality) will be assessed by comparing time from randomisation to death from any cause between randomised groups, assessed up until the end of the follow-up period, where all patients will have a minimum of 90 days follow-up.

The primary outcome (90-day mortality) will be compared between treatment arms using survival analysis methods. Kaplan-Meier survival curves will be constructed for visual presentation of the data. A Cox proportional hazards model will be fitted to obtain an adjusted hazard ratio and corresponding 95% confidence interval with p-value.

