9 TRIAL PROCEDURES

All data will be recorded in the CRFs.

The Visits will be at Baseline (D0), Day 1 (D1), Day 2 (D2), Day 3 (D3), Day 7 (D7), ICU discharge, Hospital Discharge, Day 60 (D60) (+/- 14 days) and Day 90 (D90) (+/- 14 days).

Adverse events should be recorded as soon as the Local Research Team become aware of them. Please see Section 11 **ADVERSE EVENT REPORTING** for further details.

Day 0 (D0)

- Demographics Data:
- Sex, age, height, weight, APACHE score, summary of the relevant medical history, date of admission to hospital and ICU should be recorded at randomisation
- Treatment Allocation:
- Treatment Arm
- Randomisation date and time
- Time and date of first AF will be recorded. The diagnosis of AF should be confirmed by a competent clinician.
- Components in order to calculate the SOFA score
- Clinical Data Data for the 24 hours prior to randomisation should be recorded. This can be collected from the clinical records and may be collected retrospectively.
- Cardiovascular: time and date of onset of AF and HR, Mean Arterial Pressure (MAP), Inotrope and Vaospressor type and dose every 6 hours.
- Biochemistry: Sodium, Potassium, Urea, Creatinine, Magnesium and C-Reactive Protein (CRP).
- *Haematology:* White Cell Count, Lymphocyte, Monocyte, Neutrophil and Platelet count and the haemoglobin.

Day 1 (D1), Day 2 (D2), Day 3 (D3), and Day 7 (D7)

- Clinical Data This can be collected from the clinical record and may be collected retrospectively
- Cardiovascular: time and date of onset of AF and HR, Mean Arterial Pressure (MAP), Inotrope and Vaospressor type and dose every 6 hours.
- Biochemistry: Sodium, Potassium, Urea, Creatinine, Magnesium and C-Reactive Protein (CRP).
- *Haematology:* White Cell Count, Lymphocyte, Monocyte, Neutrophil and Platelet count and the haemoglobin.
- Expected Serious Adverse Events:
- Death related to the underlying cause of ICU admission
- Cardiovascular failure, including the need for vasopressors/ inotropes
- Respiratory failure, including mechanical ventilation and acute lung injury
- Hepatic impairment as measured by Bilirubin rise of >100 μ mol/L or Transaminases >1000 μ L/L
- Acute Kidney Injury, including the need for renal replacement therapy
- Haematological / coagulation failure, including thrombocytopaenia and Disseminated Intravascular Coagulopathy (DIC)
- Delirium / confusion

Discharge From ICU

- Date of discharge from ICU
- Mortality status

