11.5 Serious Adverse Events not requiring reporting to the ABBRUPT Trial Office

Participation in the trial will be for 90 days following randomisation. At whatever time they occur during the patient's participation, from the time the intervention started to the end of patient follow-up, the following are not considered to be critical to the evaluation of the safety of the trial:

- Known complications of the underlying cause of the patient's ICU admission (not including death; please refer to section 11.6).
- Pre-planned hospitalisation(s) following patient discharge

All events which meet the definition of serious must be recorded in the patient's notes, including the causality and severity, throughout the patient's time on trial, including follow-up, but for trial purposes these events do not require reporting on the SAE Form. Such events are 'safety reporting exempt'.

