16.6 Missing data and sensitivity analyses

Every attempt will be made to collect full follow-up data on all study patients; it is thus anticipated that missing data will be minimal. Since the primary outcome is based on a time-to-event analysis, a sensitivity analysis to assess the impact of missing data will not be required since all patients will be included in the analysis and will be censored at the point where they have no further data.

There may be times when patients in both groups do not sufficiently adhere to their treatment, i.e. poor uptake of the drug, or may even be commenced on an alternative drug. To assess the impact of this, a per-protocol analysis for the primary outcome will be undertaken as a sensitivity analysis.

Full details will be included in the Statistical Analysis Plan.

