16.7 Planned final analyses

The primary analysis for the trial will occur once all patients have completed the 90-day follow-up assessment and corresponding outcome data has been entered onto the trial database and validated as being ready for analysis. This analysis will include data items up to and including the 90-day assessment and no further.

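### The protocol does not set one follow-up horizon for 90-day mortality: no cut at day 90 is stated, and an in-window final contact before day 90 breaches the promised 90-day minimum

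*Protocol*

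**What the plan says.** - **Outcome and horizon.** Protocol Section 16.3: "Differences in the primary outcome (90-day mortality) will be assessed by comparing time from randomisation to death from any cause", and this is "assessed up until the end of the follow-up period, where all patients will have a minimum of 90 days follow-up". A minimum with no maximum implies that some patients may contribute time beyond day 90.
- **Data cut.** Section 16.7: "This analysis will include data items up to and including the 90-day assessment and no further". The cut is an assessment, not a number of days since randomisation.
- **Timing of that assessment.** Section 9 sets the late visits at "Day 60 (D60) (+/- 14 days) and Day 90 (D90) (+/- 14 days"), and Table 1 repeats the window. The final contact may therefore fall anywhere from day 76 to day 104. Section 9 lists mortality status among the items collected there.
- **Length of participation.** Section 11.5: "Participation in the trial will be for 90 days following randomisation".
- **Censoring.** Section 16.6: patients "will be censored at the point where they have no further data". For the primary outcome, "a sensitivity analysis to assess the impact of missing data will not be required".
- **Design horizon.** Section 16.1 takes 90-day mortality of about 20% and a 5-point absolute difference, converts this to a hazard ratio of about 0.73, and derives 426 events, about 2430 patients, and 2560 after 5% non-evaluable.

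**The concern.** Each statement is reasonable alone, but together they do not fix which deaths are primary events.

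If the last contact is early, say day 78, the patient has been followed as the visit schedule allows but has fewer than 90 days of follow-up. Under Section 16.6 that patient is censored at day 78, and a death on day 85 may never be recorded.

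If the last contact is late, say day 100, a death on day 95 falls inside both the follow-up of Section 16.3 and the data cut of Section 16.7. It can then count towards an outcome called 90-day mortality.

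The two problems differ in kind. Late deaths can be removed at analysis, provided the date of death is held. Vital status that was not collected after an early contact cannot be restored by an analysis rule; it has to be obtained by the follow-up procedures. The protocol describes no central mortality linkage that would fill the gap.

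**Working it through.** **1. Reproduce the design figures.** Inputs from Section 16.1: two-sided alpha 0.05, 90% power, hazard ratio 0.73, mortality 20% v 15%. Allocation 1:1 is from Section 6.5.

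- Unrounded hazard ratio: ln(0.85)/ln(0.80) = 0.7283, consistent with 0.73.
- Schoenfeld: 4 × (1.960 + 1.282)² / [ln(0.73)]² = 424.4, so 425 events.
- Freedman at 0.7283: (1.7283/0.2717)² × (1.960 + 1.282)² = 425.2, so 426 events, the stated figure.
- Pooled risk (20% + 15%)/2 = 17.5%; 426/0.175 = 2434 (stated: about 2430).
- 2430/0.95 = 2558, rounded to 2560.

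The sample size is sound, and its event probability is a day-90 risk, so the design intends a fixed day-90 horizon.

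**2. Set the rules side by side for in-window final contacts.**

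| Final contact | In window (Section 9)? | 90-day minimum met (16.3)? | Consequence as written |
|---|---|---|---|
| Day 76–89 | Yes | No | Censored at contact (16.6); later deaths up to day 90 may be missed |
| Day 90 | Yes | Yes | Matches the outcome name |
| Day 91–104 | Yes | Yes | Deaths after day 90 are within follow-up (16.3) and the data cut (16.7) |

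**3. Bound the size.** The documents give neither the shape of the hazard nor the spread of contact dates, so both are assumed. Cumulative mortality in each arm is 1 − exp[−H(90) × (t/90)^k], with H(90) = −ln(0.80) or −ln(0.85). Here k = 1 is a constant hazard and smaller k puts deaths earlier. Events = 2430 × mean of the two risks. Power = Φ(½ × √events × |ln 0.73| − 1.96). Every final contact is placed on the same day, which is the extreme case.

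| k | Day | Mortality, two arms | Difference (points) | Events | Power |
|---|---|---|---|---|---|
| any | 90 | 20.0% v 15.0% | 5.0 | 425 | 90.1% |
| 1 | 76 | 17.2% v 12.8% | 4.4 | 365 | 85.2% |
| 0.5 | 76 | 18.5% v 13.9% | 4.7 | 394 | 87.8% |
| 0.3 | 76 | 19.1% v 14.3% | 4.8 | 406 | 88.7% |
| 1 | 104 | 22.7% v 17.1% | 5.6 | 484 | 93.4% |
| 0.5 | 104 | 21.3% v 16.0% | 5.3 | 454 | 91.8% |
| 0.3 | 104 | 20.8% v 15.6% | 5.2 | 442 | 91.1% |

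Share of day-90 deaths unobserved when every contact is on day 76: (425.25 − 364.5)/425.25 = 14.3% for k = 1; (425.25 − 393.8)/425.25 = 7.4% for k = 0.5; (425.25 − 406.1)/425.25 = 4.5% for k = 0.3.

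**4. After the fix.** With all patients followed to day 90 and censored there, 2430 × 0.175 = 425 events and power is 90.1%. N stays at 2560.

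**The case against.** The case for leaving the text alone is that the outcome is called 90-day mortality throughout, participation is 90 days, and ±14 days is a tolerance for collecting data, not another endpoint definition. Section 16.3 promises everyone at least 90 days, so a day-76 contact was presumably not meant to be the last word on survival. Time to death is analysed by date, so late deaths can be excluded. Cox and Kaplan-Meier methods accommodate unequal censoring. Section 16.2 calls the text an outline, and an exact censoring rule is often left to the SAP, which is not shown.

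Much of this stands. The window should not be read as a third endpoint, and Section 16.7 limits any overrun to about day 104. What does not fall away is that the stated minimum and the permitted window contradict each other within the protocol, and that an SAP rule cannot supply status that was never collected.

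Three stronger readings are tempting and are not supported:

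- **That the shift rivals the 5-point target difference.** Under a constant hazard, pooled mortality moves from about 15% at day 76 to about 20% at day 104. That movement is shared by both arms. The between-arm difference moves by only about 0.2 to 0.65 points from 5.0, even with every contact at a window edge.
- **That contact timing will differ by arm because the trial is open label.** The schedule and window are the same in both arms and run from randomisation. Nothing in the protocol points to differential timing.
- **That a hazard ratio cannot be judged against an absolute target.** Section 16.1 starts from "A 5% absolute difference in mortality is considered a" clinically important difference and itself converts it to 0.73. Section 16.2 also commits to summary proportions by group.

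**Conclusion.** The horizon for the primary outcome is internally inconsistent and should be corrected, but this is a clarification with a small procedural change, not a threat to the trial's validity. It is also not shown that 90-day mortality will in fact be incompletely observed or run past day 90; the wording permits both and prevents neither.

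The loss of roughly 5% to 14% of day-90 deaths, with power of 85–89% instead of 90%, is an outer bound. It rests on all final contacts falling on day 76, on Weibull shapes from 0.3 to 1 that the documents do not give, and on no other source of death dates after the contact. Contacts spread across the window would cost less. Under proportional hazards and non-informative censoring the hazard ratio is not biased; the cost is information, and an event set that depends on when a contact happens to be made.

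**What to change.** 1. In Sections 16.3 and 16.7, state one rule: time from randomisation to death from any cause, administratively censored at day 90, with later deaths not counted as events. Replace the reference to the end of follow-up, and align the censoring sentence in Section 16.6.
2. In Section 9 and Table 1, separate vital status from the other day-90 items. Require it to be confirmed on or after day 90 (0/+14 days), and keep ±14 days for the EQ-5D-5L and the rest.
3. Carry the same day-90 rule into the SAP.

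The cost is a protocol amendment and, for patients contacted before day 90, one later status check from records or by telephone. It is best introduced while patients are still in follow-up, since status is harder to recover afterwards. The sample size and the primary model do not change.

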16.4 Secondary outcomes

The secondary outcomes are a combination of time-to-event data, binary data, continuous data and count data.

Time-to-event outcomes: The secondary outcomes that are time-to-event data (e.g. ICU mortality and hospital mortality) will be analysed using the same methods as described for the primary outcome.

Count data outcomes: For secondary outcomes that are count data (e.g. Number of episodes of bradycardia (HR <50 bpm)), a Poisson regression model (or negative binomial mode if evidence of overdispersion) will be used for analysis. Time (in days) will be used as an offset in the model. Results will be presented as an adjusted incidence rate ratio with 95% confidence interval and p-value.

Binary outcomes: The secondary outcomes that are binary data (e.g. Rates of stroke and myocardial infarction) will be analysed using a Poisson regression model (with robust standard errors). Results will be presented as an adjusted relative risk with 95% confidence interval and p-value.

Continuous outcomes: The secondary outcomes that are continuous data (e.g. Hospital length of stay) will be analysed using a linear regression model. Results will be presented as an adjusted mean difference with 95% confidence interval and p-value.

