8.2 Main trial outcomes

Primary outcome

90-day mortality

Secondary outcomes

Clinical Outcomes

- ICU and hospital mortality
- Rates of Cardiovascular events including stroke, myocardial infarction or thromboembolism at 90-days
- Rate of established AF by the end of ICU stay / death/ day 90

Economic Outcomes

- Cost-effectiveness of the interventions
- · Health care resource use including ICU and hospital length of stay

Safety Outcomes

- The number episodes of bradycardia (HR <50 bpm) whilst in hospital and being prescribed the intervention
- Bradycardia and bradycardic arrhythmias with haemodynamic compromise requiring intervention
- Significant hypotension requiring intervention (not including temporarily stopping the trial medication) whilst in ICU
- Heart block
- Arrhythmia with haemodynamic compromise requiring intervention including DC cardioversion

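### ICU and hospital mortality are assigned to Kaplan-Meier and Cox with no rule for discharge alive, which is a competing event

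*Protocol*

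**What the plan says.** Protocol section 8.2 lists "ICU and hospital mortality" first among the clinical secondary outcomes. Section 16.4 sorts the secondary outcomes by data type and places these two under time-to-event: "e.g. ICU mortality and hospital mortality) will be analysed using the same methods as described for the primary outcome".

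Section 16.3 gives the methods referred to. The primary analysis works by "comparing time from randomisation to death from any cause between randomised groups", with at least 90 days of follow-up for every patient. For display, "Kaplan-Meier survival curves will be constructed for visual presentation of the data". For the effect, "A Cox proportional hazards model will be fitted to obtain an adjusted hazard ratio and corresponding 95% confidence interval with p-value".

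The only censoring rule is in section 16.6. It is written for the primary outcome: patients "will be censored at the point where they have no further data". The protocol does not mention discharge alive as a competing event or a cumulative incidence function. It has no rule that keeps discharged patients event-free to a fixed day.

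Section 16.4 also sets out a robust-Poisson adjusted relative risk for binary outcomes, but does not assign ICU or hospital mortality to it. Section 16.2 promises summary statistics by group for all outcomes, proportions among them.

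**The concern.** The primary outcome has no competing event: a patient who leaves ICU or hospital can still die of any cause before day 90, and that death counts. ICU mortality and hospital mortality are different. Once a patient is discharged alive, the event can no longer happen in that stay, and patients are usually discharged because they have recovered. Carrying the section 16.3 methods across leaves open what happens to follow-up at discharge. The ordinary way to fit Kaplan-Meier and Cox to death in the unit is to censor there.

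That has two consequences. Kaplan-Meier treats the discharged as if they faced the same future risk of ICU death as those still there, so one minus Kaplan-Meier is too high. The Cox hazard ratio becomes a ratio of daily death rates among those remaining, which does not translate into a ratio of risks when the arms are discharged at different speeds. ICU and hospital length of stay is itself a listed outcome, so a difference in discharge speed is something the trial sets out to examine. A reader could then be told that ICU mortality is the same when it differs, or the reverse.

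**Working it through.** **The plan's own figures.** The protocol states no ICU or hospital mortality and no length of stay, so there is no figure on this point to reproduce. The sample-size figures for the primary outcome do reproduce (425 to 426 events against 426 stated; 2430/0.95 = 2558, rounded to 2560) and are not in question. All hazards below are assumptions.

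**Formulas.** Let d be the daily hazard of death in ICU and r the daily hazard of discharge alive, both constant.
- Risk of dying in ICU over the whole stay: d/(d + r)
- Cumulative incidence of ICU death by day t: [d/(d + r)] × [1 − exp(−(d + r)t)]
- One minus Kaplan-Meier with discharge censored: 1 − exp(−d·t)
- Cox hazard ratio with discharge censored: the ratio of the two values of d

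**Illustration.** d = 0.02 in both arms; r = 0.10 in arm A and 0.08 in arm B.

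| | Arm A | Arm B |
|---|---|---|
| ICU mortality | 0.02/0.12 = 16.7% | 0.02/0.10 = 20.0% |
| Cumulative incidence, day 28 | 16.7% × (1 − exp(−3.36)) = 16.1% | 20.0% × (1 − exp(−2.80)) = 18.8% |
| 1 − Kaplan-Meier, day 28 | 1 − exp(−0.56) = 43% | 1 − exp(−0.56) = 43% |
| Still in ICU at day 28, of 1280 | 1280 × exp(−3.36) = 44 | 1280 × exp(−2.80) = 78 |

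The risk ratio (B v A) is 20.0/16.7 = 1.20. The discharge-censored hazard ratio is 0.02/0.02 = 1.00.

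**Range of the curve bias.**
- ICU, mortality 10 to 20% and mean stay 5 to 12 days: 1 − Kaplan-Meier at day 30 is 22 to 70%, against a cumulative incidence of 9 to 20%. The top of that range is thin: with a 5-day mean stay only 1280 × exp(−6), about 3 patients per arm, remain at day 30. With an 8-day mean stay (1280 × exp(−3.75), about 30 remaining) the figure is 31 to 53%.
- Hospital, mortality 10 to 20% and mean stay 20 to 30 days: 1 − Kaplan-Meier at day 90 is 26 to 59%, against a cumulative incidence of 10 to 20%.

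**Simulation of the Cox result.** 1280 per arm, 200 replicates; reference arm with mean ICU stay of 8 days and ICU mortality of 15%.

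| Scenario | ICU mortality | HR, censored at discharge (p < 0.05) | HR, discharged kept event-free to day 90 (p < 0.05) |
|---|---|---|---|
| Discharge 1.25 times faster in one arm, equal death hazard | 15.0% v 12.4% (RR 0.82) | 1.01 (3%) | 0.82 (48%) |
| Death and discharge hazards both 1.25 times higher in one arm | 15% in both | 1.25 (61%) | 1.00 (7%) |

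So the discharge-censored hazard ratio can sit near 1 when ICU mortality differs, and well away from 1 when it does not.

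**The case against.** The strongest reply is that the protocol never says discharge alive will be censored. That is true, and a reader who infers that it does goes further than the text. The section 16.6 rule censors at the last available data, and mortality status is also collected at days 60 and 90. Carried over literally, patients discharged alive could stay in the risk set, event-free, to day 90, which would be a valid comparison. But section 16.6 speaks of the primary outcome, and that treatment of discharge is nowhere written. A third reading, in which deaths after discharge also count, merely repeats the primary outcome. The text needs settling under any of the three.

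Second, section 16.2 calls this a brief outline and defers detail to the SAP, which could specify the valid treatment. This stands in part. However, the outcome class and the model are already chosen in section 16.4, and an SAP that only elaborates them would carry the problem forward.

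Third, a discharge-censored Cox model does validly estimate a cause-specific hazard, Kaplan-Meier is for display only, and crude proportions by arm will be reported. All of this stands. It limits the fault to the curves and to presenting the adjusted effect as one on ICU or hospital mortality.

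A reader might also extend the criticism to length of stay, because linear regression counts an early death as a short stay. The protocol does not support that as an error: section 8.2 lists length of stay as an economic outcome under resource use, and mean bed-days including those who die is the right quantity for it. A mean difference in stay produced by deaths is a real difference in bed-days, so detecting it is not a false positive.

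**Conclusion.** The point holds as a moderate issue for two secondary outcomes. Section 16.4 assigns ICU and hospital mortality to methods built for an outcome without competing events and gives no rule for the competing event that these outcomes have. In the ordinary application, one minus Kaplan-Meier overstates mortality (43% against a cumulative incidence of 16 to 19% at day 28 in the illustration), and the hazard ratio can miss a mortality difference or suggest one that is absent.

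The sizes rest on assumed mortality, lengths of stay and constant hazards, and on censoring at discharge. The upward direction of the curve bias does not depend on the particular values. A reader might run the illustration's curve formula on to day 90 and quote a much larger overstatement. That figure should not be used: with exit hazards of 0.12 and 0.10 per day, 1280 × exp(−10.8) = 0.03 and 1280 × exp(−9) = 0.16 patients would remain in ICU, so no usable estimate would exist.

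The primary 90-day analysis is untouched.

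**What to change.** In section 16.4, and in the SAP to match:

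- Move ICU and hospital mortality to the binary outcomes. Define them as death before ICU discharge and death before hospital discharge in the index stay, capped at day 90, and analyse them with the robust-Poisson adjusted relative risk already specified there.
- If curves are shown, plot cumulative incidence with discharge alive as the competing event, or keep patients discharged alive event-free to day 90.
- If a discharge-censored Cox hazard ratio is reported, label it cause-specific and supportive.

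The cost is a change of wording. Discharge dates and mortality status are already collected at ICU and hospital discharge (section 9), so no new data are needed. The downside is that a relative risk replaces a hazard ratio for these two outcomes.
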